After oral administration of methotrexate, its absorption occurs in the proximal jejunum, mainly through the proton-coupled folate transporter (PCFT/SLC46A1), which transports reduced folic acid and methotrexate. In addition, part of methotrexate may be metabolized to 4-amino-4-deoxy-N10-methylpara aminobenzoic acid with the involvement of intestinal bacteria. The bioavailability of methotrexate is relatively high, generally in the range of 64% to 90%, but varies widely between patients and decreases with increasing doses, with stable bioavailability at doses greater than 15 mg per week, indicating intestinal transporter saturation. Methotrexate, when taken orally, has a Cmax of between 0.3 to 1.6 µmol/L, generally occurring 0.75 to 2 hours after administration. Multiple studies have demonstrated that subcutaneous injection of methotrexate has higher bioavailability compared with oral methotrexate. Subcutaneous injection of methotrexate resulted in linear, dose-proportional increases in blood drug concentrations, with no dose saturation effect. Approximately 50% of circulating methotrexate binds to plasma protein. Methotrexate can be distributed into synovial fluid at concentrations comparable to those in plasma. Methotrexate undergoes the firstpass effect metabolism in the liver and is converted to 7-hydroxymethotrexate (7-OH-MTX), a major metabolite of methotrexate. Renal excretion is the main route of excretion for methotrexate. Methotrexate is filtered through the glomeruli, as well as active tubular secretion and reabsorption. A small portion of methotrexate is excreted through bile and a portion enters hepatic-enteric circulation. The plasma half-life of low dose of methotrexate is between 4.5 to 10 hours. The excretion of methotrexate is reduced in patients with impaired renal function, ascites, or pleural effusion, who need to be particularly careful to monitor toxic effects and may need to reduce the dose or in some cases discontinue methotrexate therapy.

Cellular uptake of methotrexate is mediated by reduced folate carrier 1 (RFC1/SLC19A1), with limited contributions from  $\alpha$  and  $\beta$  folate receptors. The

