#### 5.2.2 Exclusion Criteria

- 1. Patients not diagnosed with T-LGLL or CLPD-NK
- 2. Patients with no indication for LGLL treatment
- 3. Patients who are unable to understand or follow study procedures
- 4. Patients who have been diagnosed or treated for malignancies other than LGLL within the past five years
- 5. Patients with non-lymphoma-related hepatic and renal impairment: alanine aminotransferase (ALT)  $> 3 \times$  upper limit of normal (ULN), aspartate aminotransferase (AST)  $> 3 \times$  ULN, total bilirubin  $> 2 \times$  ULN, and serum creatinine clearance (CrCl) < 30 mL/min
- 6. Patients with other severe diseases that have an impact on this study (uncontrolled diabetes, stomach ulcers, other severe cardiopulmonary conditions, etc.), at the discretion of investigators.
- 7. High-risk patients based on the Caprini score for thromboembolism (Appendix 2)
- 8. Patients with a known history of HIV infection, or with active hepatitis B virus (HBV) infection, or any uncontrolled active systemic infection requiring intravenous antibiotics

Notes: HBV infection is considered active if all following criteria are met: a. HBV DNA quantification ≥2000 IU/mL; b. ALT ≥2 times × ULN; c. LGLL, medications, and other causes-induced hepatitis are excluded. Patients with active HBV infection at the time of initial diagnosis who are converted to inactive HBV infection after adequate anti-HBV treatment could be enrolled in this study.

- 9. Patients who have undergone major surgery (excluding lymph node biopsy) within the past 14 days or who are expected to undergo major surgery during study treatment
- 10. Pregnant or lactating women, and women of childbearing potential who have not taken contraceptive measures
- 11. Patients who are allergic to the agents or the ingredients

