# 6 Treatments

# **6.1 Treatment Regimen**

Treatment will be provided in 3-month cycles. Patients will receive thalidomide of 50 to 100 mg orally QD before bedtime, methotrexate of 10 mg/m² orally once weekly, and prednisone of 0.5 to 1 mg/kg orally QOD. Prednisone will be tapered after 3 months of dosing and dosed for up to 6 months. Methotrexate will be dosed for up to 1 year. Thalidomide will be dosed for up to 2 years or discontinued at the investigator's discretion based on clinical symptoms. Efficacy was evaluated after 3 months of treatment, if PR or above response to treatment, the initial treatment regimen will be continued. If there is no clinical benefit after 6 months of initial treatment, patients will switch to the second-line treatment was and will be withdrawn from the study.

Dosage and administration for study drugs are shown in the following table:

TPM Regimen	Dosage and Administration
Methotrexate	10 mg/m  orally, once weekly
Prednisone	0.5–1 mg/kg orally, every other day
Thalidomide	50–100 mg orally, once daily before bedtime

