#### **Methotrexate:**

Methotrexate will be administered orally at 10 mg/m^2 once weekly on a fixed day in the morning. Patients who achieve CR can discontinue methotrexate after 4 months of consolidation therapy, with a maximum duration of 1 year.

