## 7.4.2 Dose Adjustment and Discontinuation of Methotrexate

Methotrexate is contraindicated in LGLL patients with an estimated glomerular filtration rate (eGFR) <30 mL/min. For patients with an eGFR of 30 to 59 mL/min, a lower initial dosage is required; and a more gradual dose increase, close monitoring, and a lower maximum weekly dose should be considered, depending on the overall clinical conditions. Although low doses of methotrexate are not nephrotoxic, methotrexate is almost completely excreted through the kidney. Therefore, kidney function should be monitored. If renal insufficiency occurs, the methotrexate dose should be reduced or discontinued.

Guidelines from Cancer Care Ontario in Canada recommend a 25% reduction of dose at CrCl of 80 mL/min, 40% reduction at CrCl of 60 mL/min, 50% reduction at CrCl of 50 mL/min, and discontinuation at CrCl <50 mL/min. The guidelines also state that less conservative dose adjustments may be considered when using a low-dose regimen (<50 mg/m²). High-dose methotrexate could only be administered only when CrCl is >60 mL/min.

See Appendix 2 for the calculation method of CrCl.

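### Exclusion 5 ties the renal limit to the cause of the impairment, while Section 7.4.2 bars methotrexate below 30 mL/min whatever the cause

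*Supplement*

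**What the plan says.** All references are to protocol version 2.0.

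- **Entry.** Exclusion 5 in Section 5.2.2, and the same item in the synopsis, begins "Patients with non-lymphoma-related hepatic and renal impairment: alanine aminotransferase (ALT". It gives limits for ALT, AST and total bilirubin and closes with "and serum creatinine clearance (CrCl) < 30 mL/min". The cause qualifier stands at the head of the item, so it governs the renal limit as well as the liver limits.
- **Treatment.** Section 6.1 prescribes "methotrexate of 10 mg/m² orally once weekly" as one of three drugs given to all patients. Section 6.2 has it taken "once weekly on a fixed day in the morning". No methotrexate-free start is defined.
- **Contraindication.** Section 7.4.2 states: "Methotrexate is contraindicated in LGLL patients with an estimated glomerular filtration rate (eGFR) <30 mL/min". The cause of the impairment is not mentioned.
- **Pharmacology.** Section 7.4.2 says that "methotrexate is almost completely excreted through the kidney". Section 2.4 says: "The excretion of methotrexate is reduced in patients with impaired renal function". Neither statement depends on cause.

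**The concern.** An entry rule should not admit a patient whom another section of the same protocol bars from a drug in the regimen. Exclusion 5 can do this, because its renal limit applies to only some causes and the methotrexate contraindication applies to all of them.

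Such a patient would be enrolled and could not be given methotrexate. The patient's outcome would then say nothing about TPM, whose complete remission rate is the primary endpoint. Sites could also differ: one might enrol on the literal text, while another might refuse because of Section 7.4.2.

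**Working it through.** No formula or power figure is involved, so the check is a comparison of the texts.

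1. **Does LGLL-attributed impairment escape exclusion 5?** Section 2.5 describes LGLL as an indolent lymphoma. Impairment attributed to LGLL therefore reads as lymphoma-related and falls outside the qualifier.

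2. **Does another criterion set a renal limit?** No inclusion criterion in Section 5.2.1 sets a minimum renal function. Among the exclusions, only no. 11 concerns unsuitability for a study drug in general terms, and it covers allergy alone.

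3. **Are the two limits otherwise the same?** The number is the same, 30 mL/min, but two things differ:

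| | Exclusion 5 | Section 7.4.2 |
|---|---|---|
| Measure | CrCl (Cockcroft-Gault, Appendix 3) | eGFR |
| Limit | below 30 mL/min | below 30 mL/min |
| Cause | non-lymphoma-related only | any |
| Effect | no entry | no methotrexate |

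4. **Who falls in the gap?** By cause: a patient with CrCl and eGFR both below 30 mL/min, attributed to LGLL. By measure: a patient with CrCl at or just above 30 and eGFR just below 30, whatever the cause. Removing the qualifier closes only the first route.

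5. **Does the protocol give a reason for the qualifier?** None is given for the kidney. For the liver there is at least a parallel, because the hepatitis B note in Section 5.2.2 sets aside hepatitis caused by LGLL.

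6. **How many patients?** The documents give no figure. The disease description (Section 2.1) and the treatment indications (Sections 2.2 and 5.2.1) name no renal involvement by LGLL. Assuming 0 to 1 patients, for scale only, against the 42 planned in Section 4.5: 0/42 = 0% and 1/42 = 2.4%.

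**The case against.** The strongest reply is that the affected group may be empty and that the harm is already blocked. Nothing in the protocol describes LGLL causing renal impairment, and Section 7.4.2 forbids methotrexate below the limit. There are also several other ways to catch such a patient:

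- Exclusion 6 covers "Patients with other severe diseases that have an impact on this study", at the investigator's discretion.
- Section 5 requires consultation with the sponsor before enrolment when a criterion is in doubt.
- Under Section 4.6 the Steering Committee rules on situations that the criteria do not cover.
- Withdrawal criterion 9 in Section 5.3 allows treatment to be stopped in the patient's interest.

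Much of this stands, and it keeps the point minor. It does not remove the conflict. Exclusion 6 is discretionary and its examples do not include renal function. Sponsor consultation is mandatory, but only once someone sees a doubt, and exclusion 5 read literally raises none. The Steering Committee route has the same weakness. Withdrawal acts only after entry.

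A reader might infer that the protocol would expose patients with severe renal impairment to methotrexate. The documents do not support that: the contraindication in Section 7.4.2 is unconditional. A reader might also infer that a CrCl limit regardless of cause would settle the matter. It would not, because the contraindication is written in eGFR and the two measures can disagree near the limit.

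**Conclusion.** The inconsistency is certain on the text; its practical effect is not. Followed literally, exclusion 5 can admit a patient who may not receive TPM. The consequence is a possible mis-enrolment and uneven practice between sites, with no toxic exposure. The number is unknown, probably very small and possibly zero. The 0% to 2.4% rests wholly on the assumed 0 to 1 patients and is not an estimate from the documents. The finding is minor.

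The wrong appendix pointer in Section 7.4.2 is a separate clerical slip and adds no weight to this conclusion.

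**What to change.** **Change.** In Section 5.2.2 and the synopsis, take the renal limit out of exclusion 5 and make it a separate exclusion: CrCl (Cockcroft-Gault, Appendix 3) or eGFR below 30 mL/min, regardless of cause. Using both measures matches entry to the contraindication in Section 7.4.2 and closes both routes. Name the eGFR equation, since the protocol gives a formula only for CrCl. Leave the liver limits under the existing qualifier, and leave the dose-adjustment bands in Section 7.4.2 as they are.

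**Optional.** Exclusion 5 joins its limits with an and. If the liver limits are also reworded so that any one of them excludes, say that this clarifies the list. Anyone who has read the list as requiring all limits together would then exclude more patients, so this should be a deliberate choice and not a side effect.

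**Clerical.** Correct the pointer in Section 7.4.2 for the CrCl calculation from Appendix 2, now the Caprini form, to Appendix 3.

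**Cost.** One criterion is split in two places and one cross-reference is corrected. Weight and creatinine are already taken at screening (Section 8.1), so no new laboratory test is needed. A very few patients may become ineligible. Those with eGFR below 30 could not have received methotrexate anyway. The real loss is limited to patients with CrCl below 30 but eGFR at or above it whom exclusion 5 now lets in.

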#### 5.3 Withdrawal Criteria

- 1. Patients withdraw the ICFs
- 2. Patients experience PD or death
- 3. Patients experience intolerable toxicity that cannot be relieved after symptomatic treatment
- 4. Patients are unwilling to continue treatment
- 5. There was no clinical benefit for more than half a year
- 6. Delayed dosing for more than 4 weeks and patients are judged by investigators to be unsuitable for further dosing

- 7. Pregnancy
- 8. Lost to follow-up
- 9. Treatment should be discontinued based on the best interests of the patients at the investigator' discretion
- 10. Patients does not comply with the protocol, and the investigator deems it necessary to discontinue the treatment
- 11. The collaborator or regulatory authority notifies to end the clinical study.

If treatment discontinuation is due to any of the above reasons, the investigator must notify the Principal Investigator and complete the case summary page in the case report form (CRF), along with the date and reason for the treatment discontinuation. If treatment discontinuation is due to an AE, the AE will be followed up until it is resolved and stable.

# 5.4 Removal of Patients from Therapy or Assessment

Efforts must be made to complete the efficacy and safety tests at the time of treatment discontinuation as specified in the protocol, and to complete safety follow-up, with complete documentation of AEs and outcomes. The investigator may recommend or provide new or alternative treatments to the patient according to the actual conditions. Patients with non-PD should continue to be followed up for efficacy evaluation until they start a new antineoplastic therapy or have PD.

If a patient refuses to visit the study site for further visits, he/she should continue to be followed up for the collection of information about the study unless he/she withdraws consent to disclose further information or be contacted. In this case, no further evaluation should be conducted and no further information should be collected.

# 5.5 Identification Codes, Enrollment, and Screening Log of Screening

## **Failed Patients**

Patients who meet the screening failure criteria may be rescreened. For abnormal screening values leading to exclusion during the screening period, it is allowed to retest (to reassess eligibility), and discuss with the Sponsor as appropriate. The last test result obtained prior to the first dose of the study drugs will be used to determine if a patient is eligible for the study. Measurements taken closest to the first dose of the study drugs (prior to the first dose) will be used as baseline values for safety assessments and treatment decisions.

The investigator will fill out the patient identification code and enrollment log to facilitate easy identification of each patient during and after completion of the study. The completeness of this document will be reviewed by the Sponsor's site contact. Patient identification codes and enrollment logs are confidential documents and will be kept by the investigator in the study documentation. To ensure the confidentiality of

patient's information, this document should not be copied. For all study-related reports and correspondences, patients will be identified by patient identification code and age on the initial ICF. If a patient is not enrolled in the study, the date when the patient is met and the age on the initial ICF will be used.

# 6 Treatments

# **6.1 Treatment Regimen**

Treatment will be provided in 3-month cycles. Patients will receive thalidomide of 50 to 100 mg orally QD before bedtime, methotrexate of 10 mg/m² orally once weekly, and prednisone of 0.5 to 1 mg/kg orally QOD. Prednisone will be tapered after 3 months of dosing and dosed for up to 6 months. Methotrexate will be dosed for up to 1 year. Thalidomide will be dosed for up to 2 years or discontinued at the investigator's discretion based on clinical symptoms. Efficacy was evaluated after 3 months of treatment, if PR or above response to treatment, the initial treatment regimen will be continued. If there is no clinical benefit after 6 months of initial treatment, patients will switch to the second-line treatment was and will be withdrawn from the study.

Dosage and administration for study drugs are shown in the following table:

TPM Regimen	Dosage and Administration
Methotrexate	10 mg/m  orally, once weekly
Prednisone	0.5–1 mg/kg orally, every other day
Thalidomide	50–100 mg orally, once daily before bedtime

# **6.2 Administration of Study Drugs**

## Thalidomide:

Thalidomide administration will be started at 50 mg QD to observe whether there are adverse reactions such as rash and numbness of extremities, and then increased to 100 mg QD, if tolerated, for 1 week. Attention will be paid to observe adverse reactions such as peripheral neuritis. Thalidomide administration will be maintained for a total of 2 years and whether to discontinue will be determined based on the clinical symptoms. If the patient has a study drug-related adverse reaction, the dosage will be adjusted according to the dose adjustment guidelines in Section 7.4.1.

#### **Methotrexate:**

Methotrexate will be administered orally at 10 mg/m^2 once weekly on a fixed day in the morning. Patients who achieve CR can discontinue methotrexate after 4 months of consolidation therapy, with a maximum duration of 1 year.

#### **Prednisone:**

Prednisone will be administered orally at 0.5 to 1 mg/kg QOD for up to 6 months. It is recommended to take prednisone before 9:00 AM, with food or milk, to reduce stomach irritation. Take antacid between meals to help prevent peptic ulcer. The dose of oral prednisone will be tapered by 5 mg every 2 weeks after Months 3, and 5 mg every week after Month 4 until discontinuation.

# **6.3** Concomitant Medications and Supportive Care

## **6.3.1** Prophylactic Medications

Patients will be instructed not to take any additional medication (including over-the-counter drugs) during the study without consultation with the investigator. At each visit, the investigator will ask the patient about any new medication he/she is taking or has taken since the start of the study drug.

When combined with thalidomide, aspirin will be taken orally at 100 mg QD for antiplatelet therapy to prevent thrombosis.

For all patients for long-term use of low doses of methotrexate, folate supplementation (1 mg/day) is recommended to use to reduce the risk of some common methotrexate toxicities and the possibility of treatment discontinuation. The dosage of folate can be increased as needed to a maximum of 5 mg/day, depending on the reported residual symptoms. Folinate can be used to replace folate. Daily supplementation with folic acid or weekly supplementation with folinate can also prevent increases in plasma homocysteine concentration, which will be induced by methotrexate treatment without supplementation.

When combined with prednisone, calcium carbonate will be administered orally at 1 g QD and calcitriol will be administered orally at 0.25 µg twice daily to prevent osteoporosis; at the same time, proton pump inhibitor will be administered orally to inhibit gastric acid secretion and prevent gastrointestinal reactions.

Patients with positive hepatitis B surface antigen should receive routine examination of the HBV DNA copy number and be administered with anti-hepatitis B therapy (lamivudine or entecavir). Treatment in the active phase of the hepatitis B virus should be avoided. During treatment and within 6 months after treatment, lamivudine or entecavir should be administrated for prophylaxis, and hepatitis B DNA copy number quantification should be monitored during treatment (once every 1 to 2 months).

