#### 2.6.2 Potential Risks

According to the preliminary summarized clinical safety data, the adverse reactions of thalidomide combined with immunosuppressants and hormones regimen were mainly gastrointestinal reactions and peripheral neuropathy, manifested as numbness of hands and feet, loss of appetite, constipation, dizziness, etc. However, the adverse reactions were mainly Grade 1 or 2 and could be managed. The most severe toxicities of thalidomide were embryo-fetal toxicity and venous thromboembolism. Due to the risk

of embryo-fetal toxicity and venous thrombosis. Pregnant and lactating women will be excluded from the study and those who become pregnant during the study will be promptly withdrawn from the study. Due to the risk of venous thromboembolism, high-risk patients based on the Caprini score for venous thromboembolism will be excluded from this study. Patients will take aspirin concurrently with oral thalidomide to prevent venous thromboembolism and coagulation function will be monitored at the end of each cycle. The preliminary data of this study showed that except for 1 Grade 3 nausea, no other Grade  $\geq$ 3 adverse reactions occurred and all adverse reactions were clinically manageable. The safety of thalidomide combined with methotrexate and prednisone will be monitored in this study.

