## 5.2 Inclusion and Exclusion Criteria

#### 5.2.1 Inclusion Criteria

- 1. Patients who fulfill the diagnostic criteria for T-LGLL or CLPD-NK specified in the 2016 WHO Classification of Lymphoid Neoplasms [1]
- 2. Patients are fully informed about the study and willing to participate in the study and provide written ICF
- 3. Male or female, aged  $\geq$ 18 years
- 4. Treatment-naive patients, or patients treated with or relapsed from a non-methotrexate/ thalidomide-based regimen
- 5. Patients with at least one of the following indications for LGLL treatment:
  - a. ANC  $<0.5 \times 10^9$ /L, or neutropenia with recurrent infections
  - b. Hemoglobin <100 g/L, or requiring infusion of red blood cells
  - c. Platelets level  $< 50 \times 10^9 / L$
  - d. Concomitant autoimmune diseases requiring treatment
  - e. Symptomatic splenomegaly
  - f. Severe B symptoms (fever of unknown cause with body temperature over 38 °C; night sweats; weight loss of ≥10% within half a year)
  - g. Pulmonary hypertension
- 6. Patients with Eastern Cooperative Oncology Group (ECOG) score of 0 to 2 (Appendix 1)
- 7. Patients with life expectancy  $\geq 6$  months.

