## **6.3.2** Permitted Medications

The investigator may prescribe any concomitant medication or therapy deemed necessary to provide adequate supportive treatment throughout the study, including those listed below:

Standard supportive treatment (antiemetics, antidiarrheals, anticholinergics, spasmodic drugs, antipyretics, antihistamines, analgesics, and other medications designed to treat the symptoms or signs) will be administered as clinically indicated according to local standard of care and when deemed necessary by the investigator.

- Growth factor support, erythropoietin, and blood product transfusion are allowed for the treatment of symptoms or signs of neutropenia, anemia, or thrombocytopenia according to local standard of care.
- Infectious complications with documented evidence should be treated with oral or intravenous antibiotics, or other anti-infective drugs that the investigator considers appropriate for the infectious condition according to local standards

of care. If clinically indicated, the investigator may administer prophylactic anti-infective therapy to patients according to local standards of care.

- Prevention of tumor lysis syndrome (TLS): For patients with elevated risk of TLS such as high tumor load and renal impairment, adequate hydration and alkalinization should be performed during treatment according to clinical practice, and blood chemistry should be closely monitored.
- Prevention and treatment of HBV activation.
- Other medications for concomitant diseases: Treatment for hypertension, diabetes, etc.
- If a patient experiences an AE during study treatment, the investigator should provide appropriate treatment according to clinical practice, including but not limited to antiemetics, hepatoprotective drugs, drugs for increasing leukocyte, transfusion/blood products, anti-infection drugs, and drugs causing QTc prolongation.

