### Laboratory Abnormalities

Only clinically significant laboratory abnormalities requiring active management are recorded as AE or SAE on the CRF. The criteria for clinical significance are as follows:

- Laboratory abnormalities with clinical symptoms
- Laboratory abnormalities requiring dose adjustment, interruption, or termination of the study drug
- Laboratory abnormalities requiring more frequent follow-up assessments and further diagnostic investigations, etc.
- Laboratory abnormalities requiring changes in concomitant medication, therapy, or treatment

If a clinically significant laboratory abnormality is a symptom of disease or syndrome (eg, alkaline phosphatase and bilirubin are 5 × ULN associated with cholecystitis), only the diagnosis (eg, cholecystitis) needs to be recorded on the AE page of the CRF.

If a clinically significant laboratory abnormality is not a symptom of disease or syndrome, the abnormality itself should be recorded on the CRF as an AE or SAE. Observations of the same clinically significant laboratory abnormalities at each visit should not be repeatedly recorded as AEs or SAEs on the CRF unless the severity or etiology changes.

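### Aspirin 100 mg daily accompanies thalidomide with no platelet or bleeding condition, although inclusion criterion 5c admits patients because their platelets are below 50 x 10^9/L, with no lower limit

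*Supplement*

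**What the plan says.** All references are to protocol version 2.0.

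- **Aspirin order.** Section 6.3.1: "When combined with thalidomide, aspirin will be taken orally at 100 mg QD for antiplatelet therapy to prevent thrombosis". Section 2.6.2 says the same in its own terms: "Patients will take aspirin concurrently with oral thalidomide to prevent venous thromboembolism". Neither sentence is qualified.
- **Entry.** Section 5.2.1, criterion 5, reads "Patients with at least one of the following indications for LGLL treatment". Item 5c is a platelet count below 50 x 10^9/L. No lower bound is given.
- **Exclusions.** Section 5.2.2 sets no minimum platelet count and does not name active bleeding. The nearest item is number 6, which gives stomach ulcers as one example of severe disease and leaves the decision to the investigator. Item 7 excludes patients with a high Caprini score, which concerns thrombosis.
- **Risk section.** Section 2.6.2 states: "The most severe toxicities of thalidomide were embryo-fetal toxicity and venous thromboembolism". It does not list bleeding.

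**The concern.** The aspirin order and criterion 5c meet in the same patient. Someone who qualifies on a low platelet count alone is, by the text, given a platelet inhibitor whenever thalidomide is given, however low the count.

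The protocol's own safety sections suggest that the count may fall further or that bleeding may arise. Section 7.1 notes Grade 3 or 4 thrombocytopenia with thalidomide. Section 7.2 notes the same grades with low-dose methotrexate, although cytopenia there is generally Grade 1 or 2. Section 7.3 lists ulcer with possible bleeding under prednisone.

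Patient safety is at stake, together with consistent conduct across sites in a multicentre study. A cautious site would have to depart from the written order and a literal one would not. Neither has a common rule for starting, pausing or restarting. The benefit-risk text weighs thrombosis but does not set bleeding against it.

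**Working it through.** No arithmetic applies, and the plan gives no figure to reproduce. The check sets the relevant sections side by side and asks of each whether it governs the decision to start aspirin in a patient entering under 5c.

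1. **Is the order conditional where it stands?** No. Sections 6.3.1 and 2.6.2 use mandatory wording. The folate paragraph that follows in 6.3.1 is only a recommendation, so the protocol has softer wording available and did not use it for aspirin.
2. **Can 5c alone admit a patient?** Yes. One indication is enough, and 5c has no floor.
3. **Does an exclusion remove these patients?** No. Item 6 of Section 5.2.2 is discretionary and names ulcers, not platelet counts. Item 7 lowers thrombosis risk and does not address bleeding.
4. **Does the concomitant medication text help?**
   - Section 6.3.1 gives a proton pump inhibitor with prednisone. That is stomach protection, tied to a drug given for up to 6 months, while thalidomide, and so aspirin, may run to 2 years.
   - Section 6.3.2 allows blood products for thrombocytopenia, which covers a low baseline count but does not mention aspirin.
   - Section 6.3.2 also says: "If a patient experiences an AE during study treatment, the investigator should provide appropriate treatment according to clinical practice". This responds to an event during treatment. A low count that is the reason for entry is baseline disease.
   - Section 6.3.3 does not restrict aspirin by platelet count.
5. **Do the dose adjustment and stopping rules help?** Section 10.2 stops study drug for hematological toxicity that meets criteria and points to Section 7.4. Section 7.4 contains no platelet criterion, and aspirin is not among the study drugs listed in Section 6.4. Section 5.3, item 9, lets the investigator stop treatment in the patient's interest but gives no rule for aspirin.
6. **Does the laboratory text help?** Section 10.3 counts as clinically significant "Laboratory abnormalities requiring changes in concomitant medication, therapy, or treatment". That is a rule for recording adverse events. It foresees that a medicine may be changed but does not say when.
7. **Is the information for a rule already collected?** Yes. Section 5.5 takes the measurements closest to the first dose as baseline for safety assessments and treatment decisions. Section 8.2 lists platelets under Months 1 to 24, at the end of Cycle 1 and at the end of Cycles 2 to 8.

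Steps 3 to 6 turn up several partial safeguards and no condition on starting aspirin.

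**The case against.** The strongest reply is that clinicians will use judgment and that the protocol gives them room to: transfusion, the proton pump inhibitor, treatment of adverse events, withdrawal in the patient's best interest, and an Independent Data Monitoring Committee that can look at safety data monthly on request (Section 4.7). This stands in part. A reader might infer that patients with low platelets have no protection at all, and the documents do not support that. The remaining gap is narrower: none of these provisions settles whether the ordered aspirin is begun.

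A reader might also infer that platelets are checked only every 3 months, because the table in Section 8.3 lists hematology at that interval after Cycle 1. Section 8.2 has a separate list for Months 1 to 24 that includes platelets, without stating an interval, alongside the end-of-cycle lists. More frequent counts are the more natural reading, so a monitoring gap is not established.

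Two further objections are fair. No passage gives a count below which aspirin is unsafe, so any threshold is a clinical choice. And Section 2.6.2 reports no Grade 3 or higher reaction in the preliminary experience apart from one nausea. That is reassuring but does not settle the matter, because it states neither aspirin use nor baseline platelets.

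Finally, holding aspirin has a price: Section 2.6.2 ranks venous thromboembolism among thalidomide's most severe toxicities. This bears on how the rule is set. It does not justify leaving the question unanswered.

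**Conclusion.** The point holds as a safety gap in the written order: aspirin is unconditional, entry on a low count alone is allowed without a floor, and no other clause governs the start decision in that patient. It should be corrected, since the text as written directs an antiplatelet drug to patients enrolled for thrombocytopenia.

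Its size cannot be stated. The documents do not say how many patients enter under 5c. Section 2.2 says the need for treatment arises mainly from infections with severe neutropenia, so the share may be small. A reader might infer a quantified excess of bleeding, but the documents give no bleeding rate and none is claimed here. The sample size and the primary endpoint are not affected.

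The conclusion rests on reading the aspirin sentences as written, without assuming unwritten local practice.

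**What to change.** Amend Section 6.3.1 along these lines: aspirin 100 mg daily is given with thalidomide; it is not started, or is paused, while platelets are below 50 x 10^9/L [sponsor to confirm] or during active bleeding; it is started or restarted on recovery; holding aspirin does not by itself stop thalidomide, unless the investigator judges the thrombosis risk too high.

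The value 50 is an assumption. In the protocol it is a treatment indication (criterion 5c) and a marker of partial remission (Section 9.2), not a bleeding limit. The start decision uses the baseline count under Section 5.5, and pause and restart use the on-treatment counts already listed in Section 8.2. Carry the rule into Section 2.6.2 and list bleeding there as a risk to be weighed against thrombosis.

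The administrative cost is amended wording in two sections, with no new test. The clinical cost is that some thrombocytopenic patients on thalidomide plus a steroid go without the only specified drug thromboprophylaxis while aspirin is held. Excluding high-risk Caprini patients limits that risk but does not remove it, so the sponsor should set the threshold with both risks in view.
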